8.3. Interim Analyses and Data Monitoring

Not applicable.

8.4. Multicenter Studies

This is a multicenter study and data collected from all study centers will be listed.

8.5. Multiple Comparisons/Multiplicity

No adjustments for multiplicity will be made.

8.6. NT-proBNP (Cardiac) Endpoint Analyses

8.6.1. Best Response from Baseline

Best response will be derived from Baseline. All visits after the first infusion of study drug will be included. The number and percentage, with associated two-sided exact (Clopper-Pearson) 95% CIs, of subjects in each category of best response (response, nonresponse) will be presented. Refer to [Section 8](#) for details about course of the study and relative first infusion of study drug for each set of analyses.

Cardiac response as 3 categories (response, stable, and progression) will be presented in the same manner described above.

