2.2.4. Definition of Baseline

2.2.4.1. PRONTO Baseline

The PRONTO Baseline for the 6MWT distance (meters), as defined in the PRONTO SAP, is the longest distance walked prior to the first study drug infusion in the original parent study (NEOD001-201). For all other efficacy and safety parameters, PRONTO Baseline will be defined as the last non-missing assessment prior to the first study drug infusion in the original parent study.

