2.3.2.1. NT-proBNP (Cardiac) Endpoints

The following endpoints will be evaluated in the NEOD001 Safety Population and OLE Safety Population (see Section 5).

For these subjects, cardiac response, as assessed by N-terminal pro-brain natriuretic peptide (NT-proBNP), categories are defined as (modified from Table 2 in [Comenzo, 2012; Appendix 2](#)):

Response	Stable Disease	Progression
Decrease in NT-proBNP from baseline of >30% and >300 ng/L	Assessment was neither Response nor Progression	Increase in NT-proBNP from baseline of >30% and from baseline >300 ng/L

Best response is defined as the most favorable category (response, stable, or progression) across all visits. Subjects will be classified as responders or non-responders. Non-response is defined as either stable or progression.

- Cardiac best response from PRONTO and OLE baselines (see Section 2.2.4), as assessed by NT-proBNP response criteria. Best response will be over the course of the study.
- Cardiac response from PRONTO and OLE baselines (see Section 2.2.4), as assessed by NT-proBNP response criteria, at each visit
- Change and percent change from PRONTO and OLE baselines (see Section 2.2.4) to each visit in NT-proBNP

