4.6.1. PRONTO Visit Windows

PRONTO visit windows, as defined in PRONTO SAP, will be used to map the data collected in parent study (NEOD001-201).

[Table 2](#) defines the visit windows for assessments taken at 1-month intervals to be established with respect to relative day from the start of study drug in parent study.

Table 2: PRONTO 1-Month Interval Visit Windows (Days)

Months	Target Study Day ^a	Analysis Window Study Day ^a	
		Low	High
PRONTO Baseline ^b	1	Closest visit to Day 1, prior to first NEOD001 dose	
PRONTO Month 2	28	14	42
PRONTO Month 3	56	43	70
PRONTO Month 4	84	71	98
PRONTO Month 5	112	99	126
PRONTO Month 6	140	127	154
PRONTO Month 7	168	155	182
PRONTO Month 8	196	183	210
PRONTO Month 9	224	211	238
PRONTO Month 10	252	239	266
PRONTO Month 11	280	267	294

Months	Target Study Day ^a	Analysis Window Study Day ^a	
		Low	High
PRONTO Month 12	308	295	319 [EEOS Low – 1]
PRONTO EEOS ^c	338	320 [Month 12 Low + 30 – 5]	

^a Study day will be calculated from first dose date in parent study.

^b PRONTO Baseline is defined in Section 2.2.4.

^c PRONTO EEOS is defined as the visit occurring 30 (-5) days after the Month 12 infusion in parent study.

Table 3 defines the visit windows for assessments taken at 3-month intervals to be established with respect to relative day from the start of study drug in parent study.

Table 3: PRONTO 3-Month Interval Visit Windows (Days)

Months	Target Study Day ^a	Analysis Window Study Day ^a	
		Low	High
PRONTO Baseline ^b	1	Closest visit to Day 1, prior to first NEOD001 dose ^b	
PRONTO Month 3	56	14	98
PRONTO Month 6	140	99	182
PRONTO Month 9	224	183	266
PRONTO Month 12	308	267	319 [EEOS Low – 1]
PRONTO EEOS ^c	338	320 [Same definition as table 3]	

^a Study day will be calculated from first dose date in parent study.

^b PRONTO Baseline is defined in Section 2.2.4.1

^c PRONTO EEOS is defined as the visit occurring 30 (-5) days after the Month 12 infusion in parent study.

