8. EFFICACY ANALYSES

All recorded efficacy endpoint data will be presented in by-subject data listings for the OLE Safety Population.

Analyses will be produced in both NEOD001 Safety Population and OLE Safety Population, unless otherwise specified. Data, visit window, and treatment group to be used for each population as below:

1. NEOD001 Safety Population:
 - Data: Pooled data from parent and OLE study
 - Visit window: PRONTO visit window for data in parent study, OLE therapy visit window for OLE data with exclusion of OLE Baseline.
 - Treatment: Placebo and NEOD001 subjects received in NEOD001-201 study and Overall
2. OLE Safety Population:
 - Using data from OLE study only
 - Visit window: OLE therapy visit window
 - Treatment: NEOD001

Analyses in Renal Evaluable Population or Peripheral Neuropathy Evaluable Population will be presented in the same manner described above for NEOD001 Safety Population and OLE Safety Population.

Baseline in all efficacy analyses refers to PRONTO Baseline and OLE Baseline, unless otherwise specified.

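### Pooled best response is not split at the switch from placebo to NEOD001, so if parent-placebo subjects are included the Placebo and Overall columns mix treatments

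*SAP*

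**What the plan says.** SAP Section 8 plans two sets of efficacy analyses. Item 1, for the NEOD001 Safety Population, draws on both trials: "Data: Pooled data from parent and OLE study". Visits from NEOD001-201 keep their own windows, and extension visits, apart from the one serving as OLE Baseline, take the extension windows. The columns are laid out as "Treatment: Placebo and NEOD001 subjects received in NEOD001-201 study and Overall".

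Item 2, for the OLE Safety Population, uses extension data only and has a single NEOD001 column.

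Section 2.3.2.1 sets the rule: "Best response is defined as the most favorable category (response, stable, or progression) across all visits". Section 2.3.2.4 repeats it for renal response. Section 8.6.1 adds "All visits after the first infusion of study drug will be included" and sends the reader to Section 8 "for details about course of the study and relative first infusion of study drug for each set of analyses". The output is the number and percentage in each category with a Clopper-Pearson 95% interval. Section 8.9.1 applies the same method to best renal response.

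**The concern.** Study drug in the parent trial was NEOD001 or placebo, as the Protocol's summary of clinical experience (before Section 1.3) states. In the extension it is NEOD001 for everyone (Protocol 5.1). A parent-placebo subject who enters the extension therefore changes treatment partway through the pooled record. Best response takes the most favorable visit, so it can only stay the same or improve as visits are added, and nothing in 8.6.1 stops it at the switch or splits it there.

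What is at stake is the meaning of two published percentages. A column headed Placebo with an exact confidence interval will be read as a placebo response rate, and Overall in a population named for NEOD001 will be read as a NEOD001 rate. For adverse events the SAP avoids this: Section 9.3 and Table 6 keep the parent and extension periods apart and show extension events by parent arm. Best response has no such split.

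**Working it through.** The plan states no response rate or sample size on this point, so there is no figure to reproduce. The check is a reading of the text, followed by a visit count.

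**1. Who is in the pooled set.**
- Section 5 limits the NEOD001 Safety Population to subjects given NEOD001 in NEOD001-201. On that text the Placebo column would be empty.
- Section 8 item 1 lists a Placebo column for this population.
- Section 7.1 equates the population with all subjects dosed in the parent study.
- The Renal Evaluable Population in Section 5 is defined by parent-study proteinuria, with no restriction by arm.

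The planned tables need parent-placebo subjects, so the rest of the check includes them, on that condition.

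**2. Which infusion starts the count.** Section 8.6.1 points to Section 8 for this, but Section 8 names no infusion. The parent infusion is the natural inference. PRONTO Baseline is the "last non-missing assessment prior to the first study drug infusion in the original parent study", and the parent windows carry the note "Study day will be calculated from first dose date in parent study". The survival sections show the same looseness: 2.3.2.6 counts from first study drug and 8.11 from first NEOD001. Both readings, for a parent-placebo subject:

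| First infusion read as | Visits that count | Placebo column holds | Overall holds |
|---|---|---|---|
| First parent infusion | placebo visits, then NEOD001 visits | responses on either treatment | responses on either treatment |
| First NEOD001 infusion | NEOD001 visits only | responses on NEOD001 only | responses on NEOD001 only |

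The Placebo column is not a placebo rate under either reading. Overall is a NEOD001 rate only under the second, which would leave the subject's pooled parent visits unused.

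**3. Visit count for NT-proBNP.** The inputs are SAP Table 2 (parent windows for Months 2 to 12 plus EEOS), SAP Table 1 (NT-proBNP monthly and at EOS/ETD) and Protocol 3.1 (up to 36 infusions). It is assumed that NT-proBNP was taken at every monthly parent visit, because the parent schedule is not in these documents.
- Parent visits: 11 + 1 = 12.
- Extension visits: Months 2 to 36 plus EOS, 35 + 1 = 36.
- Share on NEOD001: 36 / (12 + 36) = 36/48 = 75%.
- With 12 extension visits: 12/24 = 50%. With 6: 6/18 = 33%.

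The shorter cases matter because SAP Section 10 records that the program was discontinued. The shares do not carry over to renal response, since 24-hour urine is collected only every 6 months in the extension, or about 6 to 7 assessments.

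**4. Effect on the percentage.** Let p1 be the proportion responding during placebo, p2 the proportion of the remaining subjects who first respond in the extension among those who enter it, and e the proportion of the remaining subjects who enter it. Then

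Placebo column = p1 + (1 − p1) × e × p2.

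The second term is the part first seen on NEOD001. The documents give none of these values. Purely as assumptions, take p1 = 20–40%, p2 = 10–30% and e = 60–100%:
- Smallest second term: 0.6 × 0.6 × 0.1 = 3.6 points.
- Largest second term: 0.8 × 1.0 × 0.3 = 24 points.

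This range shows the mechanism and is not an estimate for this trial.

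**The case against.** The strongest reply is Section 5: taken literally, it admits no parent-placebo subjects and the problem does not arise. That stands as a condition on the point. It is not an answer, because Sections 7.1 and 8 cannot be carried out on that definition.

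Second, showing extension data by original arm is an accepted display of early versus delayed start, and Section 8 does say that the columns follow treatment received in NEOD001-201. Relabelling by treatment sequence would deal with much of the complaint. It would still leave no NEOD001 rate in Overall and no rate for either treatment period in parent-placebo subjects.

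Third, cleaner results are already planned. Item 2 uses extension data only, although it is not split by parent arm. By-visit response (8.6.2) keeps the periods distinguishable because parent and extension windows are labelled separately. This is correct and limits the point to the pooled best-response tables.

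Three stronger readings are not supported:
- A reader might infer that a comparison of arms is biased toward no difference. No between-arm test or difference is planned for best response, and the direction would depend on NEOD001 producing additional responses.
- A reader might try to size the problem from chance responses accumulating over more visits. That concerns visit count rather than attribution, can affect both arm columns, and needs a within-subject variability that the documents do not give.
- A reader might infer that parent visits will be scored against OLE Baseline, since Section 8 applies both baselines to all efficacy analyses. Section 4.5 defines change from a post-baseline value, so that is not shown to be planned. A clarifying sentence is enough.

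**Conclusion.** The point holds, on the condition that parent-placebo subjects are in the pooled set. Pooled best response, cardiac and renal, then credits responses first seen on NEOD001 to the Placebo column. With the count starting at the first parent infusion, it also admits placebo-only responses to Overall. Neither column is the rate that its label suggests. The point is clearest for response from PRONTO Baseline.

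The size in percentage points is unknown. What can be bounded is exposure: for NT-proBNP, up to 75% of scheduled visits in the Placebo column could be on NEOD001, or 33% to 50% with 6 to 12 extension visits. The consequence is misinterpretation of a descriptive table; no type I error is involved.

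**What to change.** 1. Reconcile the Section 5 definition of the NEOD001 Safety Population with Sections 7.1 and 8, so that it is clear whether parent-placebo subjects belong to the pooled set.
2. For parent-placebo subjects, report two best responses: a placebo-period value (PRONTO Baseline, visits before the first OLE infusion) and a NEOD001-period value (OLE Baseline, visits after the first OLE infusion). Base any overall NEOD001 rate on visits after each subject's first NEOD001 infusion. Label any combined column by sequence, placebo then NEOD001. Do the same for renal best response.
3. Name the first infusion that 8.6.1 relies on, and state that OLE Baseline applies only to visits after the first OLE infusion.

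The cost is SAP wording and slightly more table work, with no new data. There is a downside. The placebo period has at most 12 scheduled NT-proBNP visits and the NEOD001 period up to 36, while parent-NEOD001 subjects may have up to 48. A longer period gives more chances to respond, so the period rates are not directly comparable. Show visits or follow-up per period beside each rate, or use a common follow-up length.

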8.6.2. Response at Each Visit

Response from baseline at each visit will be analyzed in the same manner described [Section 8.6.1](#).

8.6.3. NT-proBNP Endpoint: Change from Baseline

Change from baseline will be analyzed using a REML based MMRM model including a fixed effect for categorical time point and with the baseline value included as a covariate. The unstructured covariance model will be used. If the computational algorithm fails to converge, the following structures will be executed: heterogeneous Toeplitz, Toeplitz, heterogeneous First-Order Autoregressive [AR(1)], AR(1), heterogeneous compound symmetry (HCS), and compound symmetry (CS). The covariance structure converging to the best fit, as determined by Akaike’s information criterion (AIC), will be used. The Kenward and Roger method will be used to calculate the denominator degrees of freedom for the test of fixed effects. All visits will be

included in the model. Estimates of least-square (LS) means, standard errors (StdErr), and 95% CIs will be presented at each visit.

Descriptive statistics for NT-proBNP, change from baseline, and percent change from baseline will be presented by visit.

8.7. Quality of Life Endpoint: SF-36V2

PCS score, change from baseline, and percentage change from baseline will be analyzed in the same manner described in [Section 8.6.3](#).

8.8. Functional Endpoint: 6WMT Distance

Subjects will be ranked at each visit ordered from worst to best, based on the completed distance. No imputations for missing data will be made.

Descriptive statistics for 6MWT distance, change from baseline, and percent change from baseline will be presented by visit. The change from baseline at each visit in 6MWT distance will be analyzed using a rank ANCOVA model including the ranked baseline value as a covariate. Estimates of least-square (LS) means, standard errors (StdErr), and 95% CIs will be presented by at each visit.

Only valid assessments 6MWT distance will be included in analysis. Reasons for results being invalid will be presented in a listing and will be finalized prior to database lock. Reasons for results being invalid may include:

- Incorrect course length
- Use of unapproved course
- Unapproved administrator of test
- A site staff member has stopped the stopwatch either inadvertently or incorrectly before the 6 minutes are complete and the subject is still able to walk

Descriptive statistics for observed value, change from baseline, and percent change from baseline will also be presented by visit.

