8.4 Analysis of Efficacy Endpoints

Response rates will be summarized including 95% confidence intervals. The distributions of time-to-event endpoints (progression-free survival, overall survival) will be summarized using the Kaplan-Meier method.

All quantitative endpoints (except 6MWT distance) defined as the change from baseline will be analyzed using linear mixed models for repeated measurements (MMRM). The dependent variable will be the change from baseline at each time point. The model will include fixed effects for time point and treatment-by-time interaction. The baseline value of the corresponding endpoint will be included as a covariate and the unstructured covariance model will be used. The denominator degrees of freedom will be estimated using the Kenward-Roger approximation. The 6MWT distance change from baseline will be analyzed using a Wilcoxon signed rank test.

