2.2.4.2. OLE Baseline

The OLE Baseline for the 6MWT will use the PRONTO Baseline for 6MWT. Otherwise, OLE Baseline is defined as the last assessment prior to first infusion in the OLE.

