10. CHANGES TO PROTOCOL PLANNED ANALYSES

Due to the discontinuation of the NEOD001 program, the following changes were made to any protocol planned analyses:

1. All safety analyses were removed except AE overview, TEAEs and SAEs.
2. The below efficacy analyses were removed:
 - Change from baseline in troponin T
 - Change from baseline in the Short Form-36 Health Survey version 2 (SF-36v2) Mental Component Score (MCS) and the 8 subscales
 - Progression-free survival
 - For renal-evaluable subjects:
 - Time to eGFR:
 - Time to any worsening in CKD Stage
 - Time to 40% reduction in eGFR
 - Time to doubling of creatinine
 - For peripheral neuropathy-evaluable subjects:
 - Peripheral neuropathy best response
 - Peripheral neuropathy response
 - For subjects with painful peripheral neuropathy in Study NEOD001-201 (i.e., baseline Visual Analog Scale – Pain Intensity [VASPI] score >0) change from baseline in the VASPI score
 - For hepatic-evaluable subjects:
 - Hepatic response
 - Hepatic best response from baseline
 - Frequency and duration of hospitalizations over the course of the study
 - Change from baseline in the Kansas City Cardiomyopathy Questionnaire (KCCQ) subscores and overall summary score
 - Time to progression for each organ (cardiac/NT-proBNP, renal, peripheral neuropathy, hepatic) separately and to any organ progression
 - Eastern Cooperative Oncology Group (ECOG) Performance Status and New York Heart Association (NYHA) Class at each visit including any changes from baseline
 - Change from baseline in serum free light chains (sFLCs), serum and 24-hour urine protein electrophoresis (PEP), and serum and urine immunofixation electrophoresis (IFE)
 - Severity of disease-related symptoms including any changes from baseline

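### 6MWT: the SAP swaps the protocol's signed rank test for a rank ANCOVA of unstated response scale, and its OLE Baseline is only the PRONTO Baseline again

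*SAP*

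**What the plan says.** **Method.** Protocol 8.4 states: "The 6MWT distance change from baseline will be analyzed using a Wilcoxon signed rank test". That is a one-sample test of whether distance has changed.

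SAP 8.8 plans something else. It first says "Subjects will be ranked at each visit ordered from worst to best, based on the completed distance". Its model sentence then reads: "change from baseline at each visit in 6MWT distance will be analyzed using a rank ANCOVA model including the ranked baseline value as a covariate". LS means, standard errors and 95% CIs follow at each visit. Ranked baseline is the only model term named. The scale of the response and of the LS means is not given. The same section also plans summaries in metres: "Descriptive statistics for 6MWT distance, change from baseline, and percent change from baseline will be presented by visit".

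SAP Section 10 is introduced with "the following changes were made to any protocol planned analyses". It lists removed analyses only, and the 6MWT method is not mentioned.

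**Groups.** Under SAP Section 8, the OLE Safety Population is one group (NEOD001) analysed with OLE data only. The other set of analyses has columns for the parent-study arms and Overall.

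**Baselines.** For 6MWT, the PRONTO Baseline "is the longest distance walked prior to the first study drug infusion in the original parent study". SAP 2.2.4.2 then says "The OLE Baseline for the 6MWT will use the PRONTO Baseline for 6MWT", and continues: "Otherwise, OLE Baseline is defined as the last assessment prior to first infusion in the OLE". SAP 2.3.2.3 asks for 6MWT change from both baselines, and Section 8 makes both the default for efficacy. Footnote 17 of the schedule of assessments (Table 1 in both documents) requires two 6MWTs before OLE dosing, the second on Day -2 or Day -1.

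**The concern.** The signed rank test asks whether subjects walk further or less far than at baseline. A rank ANCOVA is built to compare groups after adjusting for baseline rank. The OLE Safety Population has no second group, so it is unclear what such a model would estimate there. Because the response scale is not stated, two programmers could follow 8.8 and produce tables on different scales, one of them uninformative about change. With no entry in Section 10, a reader of the report would not learn that the protocol's test had gone.

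The baseline definition raises a second problem. The study is meant to evaluate long-term treatment, and a table of change from OLE Baseline will be read as change since OLE dosing began. For 6MWT it would not be that.

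**Working it through.** The documents give no sample size basis, SD or 6MWT result, so there is no plan figure to reproduce. The first step is algebra; the simulated values only illustrate it.

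**1. LS mean for one group.** In a regression with an intercept and one covariate, the LS mean at the covariate mean equals the mean of the response. What it shows depends on the response:

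- Integer ranks within a visit (ties averaged): mean = (1 + 2 + ... + n)/n = (n+1)/2.
- Standardised ranks, rank/(n+1): mean = [(n+1)/2]/(n+1) = 0.5 for every n.
- Change in metres: mean = the observed mean change.

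Adding the same number of metres to every subject leaves all ranks as they were, whether change or distance is ranked. On either ranked response a common change therefore cannot move the LS mean.

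**2. Numerical check.** Assumed, not from the documents: baseline mean 350 m with SD 100 m, and SD of change 60 m. n = 100 is the planned enrolment. Integer ranks are used, and the signed rank p-values come from the same data.

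| Common shift (m) | LS mean, ranked change (95% CI) | LS mean, ranked distance (95% CI) | LS mean, change in metres | Signed rank p |
|---|---|---|---|---|
| -100 | 50.5 (44.7 to 56.3) | 50.5 (47.6 to 53.4) | -100.4 | 2e-17 |
| -50 | 50.5 (44.7 to 56.3) | 50.5 (47.6 to 53.4) | -50.4 | 1.6e-12 |
| 0 | 50.5 (44.7 to 56.3) | 50.5 (47.6 to 53.4) | -0.4 | 0.81 |
| +50 | 50.5 (44.7 to 56.3) | 50.5 (47.6 to 53.4) | +49.6 | 1.5e-12 |
| +100 | 50.5 (44.7 to 56.3) | 50.5 (47.6 to 53.4) | +99.6 | 1e-17 |

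At n = 50 and n = 20 the ranked LS means are 25.5 and 10.5, again for every shift.

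**3. Two parent-study groups.** With change ranked across both groups and a group term added (50 per group), the LS means were 49.8 and 51.2, a difference of 1.4 ranks. They were identical at common shifts of -100, 0 and +100 m. A group contrast can carry information, but a change shared by both groups still does not show. SAP 8.8 names no group term.

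**4. The two baselines.** Let D be the distance at an OLE visit, B the PRONTO Baseline and S the last valid OLE Screening walk.

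- Change from PRONTO Baseline = D - B.
- Change from OLE Baseline under 2.2.4.2 = D - B. The difference between the two is 0 m for every subject at every OLE visit.
- D - B = (S - B) + (D - S), that is, parent-period change plus OLE-period change. No planned analysis reports D - S.

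Example: a parent-period change of -30 m and an OLE change of 0 m give a change from OLE Baseline of -30 m. For a former placebo subject, all of that -30 m arose before the first dose of NEOD001.

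**5. How much of the interval is OLE time.** Assume OLE dosing starts at the PRONTO end-of-study target, Day 338 (SAP Table 2). Month 6-Day 1 falls 5 x 28 = 140 days after the first OLE dose, and 140/(338 + 140) = 29%. Month 12-Day 1 falls 11 x 28 = 308 days after it, and 308/(338 + 308) = 48%. With an assumed 60-day gap, the shares are 140/538 = 26% and 308/706 = 44%. These are shares of elapsed time, not of change.

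**The case against.** The strongest reply is that the harm in the model depends on a reading the SAP does not fix. The ranking sentence in 8.8 ranks completed distance, not change, and in the model sentence only baseline is called ranked. If change stays in metres, the LS mean is the mean change with a 95% CI. What then remains of the method point is an unrecorded switch of method. This stands as a limit on the claim. It does not remove the point: a ranked response is the usual meaning of a rank ANCOVA, and the flat LS mean follows whether change or distance is ranked.

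A reader might also infer that 6MWT change would go unseen. It would not: means, medians and spread of change in metres are planned by visit. What is lost on the ranked reading is the inference that the protocol planned. A reader might further infer that dropout would look like decline, since (n+1)/2 falls with n. That holds only for integer ranks; standardised ranks stay at 0.5, and the SAP does not say which it uses.

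On the baseline, 2.2.4.2 is an explicit exception, so it cannot be called a slip. For subjects given NEOD001 in the parent study, the PRONTO Baseline is the only one before any drug, and change from it suits a long-term objective. That supports keeping the PRONTO-baseline analysis. It does not support presenting the same number again under an OLE label.

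Finally, this is an uncontrolled extension with no sample size basis and no multiplicity control, from a discontinued programme. No confirmatory claim depends on the 6MWT result.

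**Conclusion.** The point holds in a conditional form for the model and without condition for the baseline.

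- **Certain:** the SAP replaces the protocol's signed rank test, does not record this in Section 10, and does not state the response scale.
- **Conditional:** if the response is ranked within visit, the LS mean for a single group (OLE Safety Population or Overall) is (n+1)/2 or a constant. It cannot show a change common to all subjects, whatever its size. If the response is change in metres, this problem does not arise. The documents do not support saying flatly that the planned analysis fails to measure change.
- **Certain:** at OLE visits the two 6MWT changes are identical, and none measures change from the start of OLE dosing. For former placebo subjects, the change labelled OLE includes the whole placebo period.

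The algebra needs no SD or retention assumption. The p-values and interval widths in the table do rest on the assumed SDs, and the time shares on the assumed start of OLE dosing. The point is worth correcting but limited to one functional endpoint, with descriptive change in metres still planned.

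**What to change.** 1. Restore the signed rank test on change in metres at each visit, with a Hodges-Lehmann or mean change and its 95% CI. If a rank ANCOVA is kept, state the response and rank scale, add a parent-group term, limit it to the comparison of parent-study groups, and record and justify it in Section 10.
2. For the OLE-baseline analysis, apply the SAP's general rule to 6MWT: the last valid walk before the first OLE infusion, taken from the OLE Screening walks. This would also agree with the use of OLE data only in the OLE Safety Population.
3. Keep change from PRONTO Baseline as a separate view, labelled as covering the parent study and the OLE. If the sponsor prefers not to redefine the OLE Baseline, dropping the duplicate removes the mislabelling, but change since OLE dosing is then still not reported.

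The cost is a few lines in SAP 2.2.4.2 and 8.8, one entry in Section 10 and a short program change. No new data are needed, since the protocol already requires the OLE Screening walks.
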